11.3. Suspected Unexpected Serious Adverse Reaction (SUSAR) Report

In the event a Suspected Unexpected Serious Adverse Reaction (SUSAR) occurs during the clinical trial, the principal investigator (PI) will report to the Institutional Review Board (IRB) to determine whether to continue or stop the study, and the main PI will report to the Minister of Food and Drug Safety (MFDS) within a period described below.

- 1) Unexpected Adverse Drug Reaction causing death or life threatening conditions will be reported immediately. The coordinating principal investigator will report it to MFDS within 7 days of awareness by phone calls, Fax, or report forms. Full documentation will be reported within 15 days of awareness.
- 2) Other unexpected and serious adverse drug reactions will be reported within 15 days of awareness by the coordinating principal investigator.
- 3) The coordinating principal investigator will report follow-up report with additional safety information until the AE is resolved (or until lost to follow-up). At this time, the investigator will actively cooperate in providing data and information on the report.

Confidential

MDR-END v14.0, 20Mar2020

12. Monitoring

12.1. Installation of Data and Safety Monitoring Board (DSMB)

- A DSMB composed of two respiratory specialists (including one who has MDR-TB experience, if available) and one statistician from other institutes having no conflict of interests will be formed.
- The DSMB may review data on side effects in the middle of the study, and may provide recommendations such as change, continuation or stopping of protocols to the investigators based on the results.

12.2. Monitoring Plans

- The coordinating principal investigator will be responsible for monitoring. Doctors and nurses, not participating in this study and having abundant clinical trial experience, designated by the main principal investigator will check GCP compliance, protection of study subjects, and accuracy of data by source document verification (SDV) of the study per each 50 subjects (i.e., when 50, 100).
- AE, unexpected problems and noncompliance of protocols discovered through DSMB will be reported by the coordinating principal investigator to Institutional Review Board(IRB) according to the regulations and the SOPs of the Human Research Protection Program (HRPP) of Seoul National University Hospital and each site.
- The respective investigator should take corrective action to resolve issues identified during the monitoring process, and cooperate with the monitoring personnel to implement countermeasures to prevent the recurrence of the issue. In the event that compliance is not achieved, the respective investigator's participation in the study will be discontinued.

13. Ethical Considerations of the Study

13.1. Compliance of Study Ethical Regulations

1) Duties of the Investigator

Investigators will be responsible for guaranteeing that the clinical study is conducted according to the protocols, the most recent International Conference on Harmonization of Technical Requirements for Enrollment of Pharmaceuticals for Human Use (ICH), the tenets of Good Clinical Practice (GCP) and relevant regulations.

GCP is a set of internationally-recognized ethical and scientific quality requirements that must be followed when designing, conducting, recording and reporting clinical trials that involve people. GCP compliance from the Helsinki Declaration provides public assurance that the rights, safety and well-being of human subjects involved in research are protected, and that it is officially guaranteed that the clinical trial data are reliable.

2) Institutional Review Board(IRB)

Prior to beginning trials, investigators will submit all of the most recent documents listed below to the IRB.

- ① Final protocol and if applicable, amended protocol
- ② Subject informed consent form (and all other documents provided to subjects)
- ③ Investigator's brochure (or equivalent information) and revised versions
- ④ Tools for recruiting subjects
- ⑤ Information on compensation for damages related to the study and, if applicable, information on financial compensation for participants of the study
- ⑥ Resume or equivalent information of the investigator
- ⑦ Study funding, sponsor name, related institutes and information on other potential conflict of interest elements and those related to compensation of subjects
- ⑧ All other documents required by the IRB to fulfill its responsibilities

This trial will begin after receiving full approval by the IRB for the final protocol, amended protocol (if applicable), subject informed consent form, applicable recruitment tools and subject compensation programs.

When necessary, investigators will submit the following documents during clinical trials to the IRB for review and approval.

- ① Amended version of the protocol
- ② Revised version of subject informed consent form and written tools provided to the subjects
- ③ If applicable, all new or revised subject recruitment tools
- ④ Compensation for damages related to the clinical trial and, if applicable, revisions on financial

Confidential

MDR-END v14.0, 20Mar2020

- compensation for participants of the studies
- ⑤ Revisions or the latest version of clinical trial data book
- ⑥ Summary of the clinical trial situations (at least once a year or when otherwise specified by the IRB)
- ⑦ Report of serious and unlisted adverse events related to the test drugs
- ⑧ New information that can have an adverse effect on the safety of subjects or clinical execution
- ⑨ Change and modification of the protocol to remove immediate threat elements to subjects
- ⑩ Report of death of subjects under the administration of the investigator
- ⑪ Notification in the case that a new clinical investigator from the trial institute becomes the principal investigator

- All other requirements of the IRB

In the case of changes to protocol that may increase threats to subjects, the changes and the corresponding revised version of the subject informed consent form will be submitted to the IRB for review and approval to apply the changes.

Once the trials are complete, the investigators will notify the IRB of the time that the trial has ended.

13.2. Obtaining written informed consent from Subjects

- Each subject will fill out the consent form according to relevant regulations after sufficiently listening to explanations on this clinical trial, and the consent forms must be signed prior to beginning any activities related to the trial. The consent form will be used after being approved by the IRB. Investigators are to draft the subject informed consent form in accordance with the Helsinki Declaration, current ICH and GCP guidelines, and relevant regulations.
- Prior to commencing trials, the principal investigator and co-investigators will explain to potential subjects the purpose and method of the clinical trial, reasonably expected benefits of the trial and potential risks and all associated discomforts. Subjects will be notified that participation is voluntary and that they may retract their consent at any time, and that even if the subject does not participate in the clinical trials, it will not affect treatment of their current diseases. Subjects will also be notified that there may be other treatment regimens available even if they deny participation, and that denying participation will not affect their treatment in the future. Lastly, subjects will also be notified that the investigator will hold the subject's personal information for long-term follow-ups, and that there will be no infringement on the subject's privacy within the allowable range of the corresponding laws and regulations, and that the institute and relevant investigators reserve the right to peruse the information. The subject's signature on the informed consent form is deemed to allow such provision of information by the subject or their legal representative.
- Subjects and/or their legal representative will be given sufficient time and opportunity to look over and ask questions about the informed consent form, and after listening to the explanation and prior to participating in clinical trials, the subject and their legal representative will be instructed to properly record their signature and date on the consent form. After receiving the consent form, the principal investigator and co-investigator will issue a copy of the consent form to the subjects.

Confidential

MDR-END v14.0, 20Mar2020

13.3. Protection of Personal Records

- Collection and operation of personal information of the subjects who participate in this study will be limited to only information necessary for the efficacy, safety and tolerability evaluation of the study drugs. Such data will be collected and operated taking precautions for compliance to laws on privacy protection and to guarantee confidentiality.
- The investigator will guarantee the following contents for personal information.
 - ① Be operated fairly and legally
 - ② Collected for a clear and fair purpose, and will not be operated in methods inappropriate for such purpose
 - ③ Will be collected appropriately and relatively, and will not exceed the mentioned purpose
 - ④ Possess accurate, and if necessary, the latest information
- The investigators must receive clear consent for use of personal information from participating subjects prior to collection of data. Such consent will mention that it may be passed on to other institutes or countries.
- Subjects have the right to request their personal information from the investigator and reserve the right to request revision of inaccurate or incomplete information. For such a request, reasonable procedures must be completed considering the essence of the request, trial situation, and relevant laws and regulations.
- Appropriate technical and structural methods must be established to protect personal information from unauthorized viewing, disclosure, accidental or illegal destruction, or coincidental loss or change. Personnel requiring access to personal information will agree to confidentiality on the identities of the subjects.
- Information collected for the study will be stored as a password-protected file in a lab with a locking device. Access to the research files will be limited to authorized investigators.

13.4. Compensation and Indemnities Provided to Subjects

No monetary compensation will be given for participating in this clinical trial. However, transportation costs used for visiting the trial institute by subjects will be compensated for at 100,000 KRW each at the time of completing the intensive phase and when completing treatment. In the case of AE caused by the investigational product or to correct and handle adverse events that may have occurred, the principal investigator will appropriately treat damages caused directly by the clinical trial drug and provide compensation to trial subjects according to the 'Rules on Victim Compensation'.

Confidential

MDR-END v14.0, 20Mar2020

14. Administrative Requirements

14.1. Change of Study Protocols

- Investigators are not allowed to change the protocols without official amendment procedure. All amended versions of study protocols must be issued by the investigator and be signed and dated. If the IRB or the relevant authorities may find basis for disapproval of the amendment, the amended protocol must not be applied unless there is need to immediately remove risks against subjects (in this case, the amended version must be submitted to the IRB and competent authorities immediately). When changes are on the managerial or administrative procedures of the trial, it can be notified only to the IRB.

14.2. Subject identification log and screening/enrollment log

- During or after trials, investigators will record subject identification log to easily identify each subject.
- The subject identification log will be dealt with confidentially, and investigators will store them in the trial institute files. No copies will be maintained for the sake of the confidentiality of subjects. All reports and exchange of information regarding the trials will mark subjects by only their initials or assigned numbers.
- Investigators will record a subject screening/enrollment log. This is a document for all subjects to determine eligibility of this trial.

14.3. Completing Case Report Forms (CRF)

- All data related to the study will be entered in the case report forms (CRF). Excluding results for tests conducted outside of the investigator's office, CRF will be completed upon the subject's visit, and the latest observations will be reflected for subjects who participated in the trials.
- All subjective evaluations recorded in CRF will, whenever possible, be continuously performed by the person who made the initial evaluation. Investigators will confirm that all information recorded in the CRF is consistent with the corresponding source document (SD).
- All inputs, edits and changes of CRF will be carried out by the investigator or delegated personnel.
- Data entry will be made directly in the e-CRF (www.phactax.org) constructed at the request of the Medical Research Collaborating Center(MRCC) and management of data will be performed by the MRCC.

14.4. Quality Assurance of Data

The process to guarantee the accuracy and reliability of data will include selection of qualified investigators and study institutes, as well as review of protocol procedures by all investigators, and delegated persons.

Confidential

MDR-END v14.0, 20Mar2020

14.5. Storage of Records

- The investigators/institutes will store essential documents in accordance to ICH/GCP E6 part 8, KGCP part 9 and relevant laws and regulations. The investigator/institute will take necessary measures to prevent loss or discarding due to accidents.
- Study documents, including essential documents, must be stored for at least three years from the date of study completion. These documents may be stored for a longer period at the request of the administrative authority.
- In the event that the investigator responsible for archiving retires, is repositioned, or cannot fulfill the responsibility for storing the study documents due to any other reason, the duty of archiving will be handed over to another person qualified to fulfill the said duties.
- The coordinating principal investigator determines the retention period of research documents of each institution and disposal after the expiration, and the detailed procedure follows the internal disposal regulation of each institution.

14.6. Completion and Stopping the Study

- Completion of Study

The study is defined as being completed when the final visit of the last subject participating in this study has been completed.

- Stopping of the Study

The investigator may close the trial site at any time when there is a feasible reason, and it must be notified sufficiently prior to termination. Reasons for closing the trial site or termination of the study are defined as follows.

- ① When the investigator does not comply with protocols or GCP guidelines
- ② Safety issues
- ③ Sufficient data to prove the lack of efficacy
- ④ Inappropriate recruitment by investigator

15. References

1. WHO. Global tuberculosis report 2014.
2. Collection of Tuberculosis Patient Report Status 2013.
3. Kwak et al, Changes in treatment outcomes of multidrug-resistant tuberculosis, *Int J Tuberc Lung Dis* 19(5):525-530
4. van der Werf M, Ko ðmo ñ C, HolloV, SandgrenA, Zucs P. Drug resistance among tuberculosis cases in the European Union and European Economic Area, 2007 to 2012. *Euro Surveill* 2014; 19: 20733. .
6. Nathanson E, Gupta R, Huamani P, Leimane V, Pasechnikov AD, Tupasi TE, Vink K, Jaramillo E, Espinal MA. Adverse events in the treatment of multidrug-resistant tuberculosis: results from the DOTS-Plus initiative. *Int J Tuberc Lung Dis* 8(11):1382-1384
7. Kang , Choi Y J, Cho Y J, et al. Cost of treatment for multidrug-resistant tuberculosis in South Korea. *Respirology* 2006; 11: 793–798.

2.1 Objective

The purpose of this clinical trial is to compare the efficacy of a new treatment regimen including Delamanid, Linezolid, Levofloxacin, and Pyrazinamide for 9 or 12 months (investigational arm) and the standard treatment regimen including injectables for 20 to 24 months (control arm) for treating fluoroquinolone-sensitive multidrug-resistant tuberculosis (TB) patients through a phase 2/3, multicenter, randomized, open-label, clinical trial.

2.2 Design

Multicenter, randomized, open-label, two arms, phase II clinical trial.

2.3 Sample Size Justification

2.3.1 Sample Size

The hypothesis of this study is that the treatment success rate at 24 months of treatment for multidrug-resistant TB using the new regimen including new anti-TB drugs will not be inferior to conventional treatment regimen (Non-inferiority test). Presumptions when calculating sample size are as follows.

- 1) The level of significance, $\alpha=0.025$ (one-sided test)
- 2) The type II error (β) set at 0.20 to maintain 80% for the power of the test
- 3) The ratio of the number of subjects (control arm investigational arm) = 1 : 1
- 4) Primary outcome: treatment success rate at 24 months after the initiation of treatment
- 5) The hypothesis of the study is as follows.
 - ① Null hypothesis: Treatment success rates of the four-drug regimen at 24 month are inferior to those of the conventional treatment. ($H_0: P_T - P_c \leq \delta$).
 - ② Alternative hypothesis: Treatment success rates of the four-drug regimen at 24 month are not inferior to those of the conventional treatment. ($H_1: P_T - P_c > \delta$).

Based on the study result of Kwak et al, 'Changes in treatment outcomes of multidrug-resistant tuberculosis, Int J Tuberc Lung Dis 19(5):525-530'(3), presuming 24 month treatment success rate of control arm as 80% and 24 month treatment success rate of investigational arm as 90%, the

noninferiority margin (δ) is -0.10 which is regarded as non-inferior when the difference is less than 10% between the two arms. The number of study subjects is 48 per arm.

Additionally, reflecting 1) proportion of fluoroquinolone-susceptible MDR-TB among participants with positive Xpert MTB/RIF assay of 50%, and 2) anticipating 5% lost to follow-up, the final number of participants is calculated as $N/(0.50*0.95)$, resulting in 102 persons per arm, 204 in total.

If a participant withdrew for any reasons within two weeks after enrollment, the participant will be replaced. Considering the number of replaced participants, the enrollment accrual ceiling is 220 persons maximum.

3. Statistical Analysis Plan

3.1 General Principle of Result Analysis

Data obtained from subjects through clinical trial will be analyzed by mITT (modified Intention-To-Treatment) analysis and PP (Per-Protocol) analysis. Efficacy evaluation will be based on a mITT (modified Intention-To-Treatment) and additional analysis on PP (Per-Protocol) group. Safety analysis will be performed on mITT, PP and the safety group (study drug administration group).

Subject Group	Definition
mITT	
- The mITT group includes participants who are randomized after satisfying eligibility criteria and receive study drugs at least one time. The subjects are not confirmed to be additionally resistant to fluoroquinolone, mono-resistant to rifampicin, or susceptible to rifampicin.

PP	
The PP (Per-Protocol) group includes participants that satisfy the following among the mITT group.
 
When completing over 80% of the planned treatment
 
: For control arm, 64 weeks or longer treatment; For investigational arm, 32 weeks or longer treatment in the 9-month treatment group and 42 weeks or longer treatment in the 12-month treatment group

Safety	
Participants who completed the study per protocol during the clinical trial period
 
: More than 80% of the planned period before treatment is completed, the following cases are considered protocol violation and excluded from the analysis group
 
① withdrawal or death.② The sputum test before culture conversion was not conducted③ Administration of study drug in the control arm 
The Safety analysis group includes participants who have taken study drugs at least one time.
 
: Evaluation based on the administration of study drug (delamanid or linezolid)

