6.3. Reversion

When *Mycobacterium tuberculosis* (MTB) is cultured at least two or more times after negative conversion.

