6.4. Treatment Outcome Definitions

Definitions of treatment outcomes refer to 2014 WHO Guidelines (20). For investigational group, 6 months will be considered as intensive phase.

<Definitions of treatment outcomes for drug-resistant patients>

TREATMENT OUTCOME	DEFINITION
Cured	Treatment completed as recommended by the national policy without evidence of failure AND three or more consecutive cultures taken at least 30 days apart are negative after the intensive phase. ^a
Treatment completed	Treatment completed as recommended by the national policy without evidence of failure BUT no record that three or more consecutive cultures taken at least 30 days apart are negative after the intensive phase. ^a
Treatment failed	Treatment terminated or need for permanent regimen change of at least two anti-TB drugs because of: 
•Lack of conversion^b by the end of the intensive phase^a; or•Bacteriological reversion^b in the continuation phase after conversion^b to negative; or•Evidence of additional acquired resistance to fluoroquinolones or second-line injectable drugs; or•Adverse drug reactions.

Died	A patient who dies for any reason during the course of treatment.
Lost to follow-up	A patient whose treatment was interrupted for two consecutive months or more.
Not evaluated	A patient for whom no treatment outcome is assigned. (This includes cases “transferred out” to another treatment unit and whose treatment outcome is unknown).
Treatment success	The sum of Cured and Treatment completed.

^a For Treatment failed, lack of conversion by the end of the intensive phase[†] implies that the patient does not convert within the maximum duration of the intensive phase[†] applied by the programme. If no maximum duration is defined, an 8-month cut-off is proposed. For regimens without a clear distinction between intensive and continuation phases, a cut-off eight months after the start of treatment is suggested to determine when the criteria for Cured, Treatment completed and Treatment failed start to apply. (†For investigational group, 6 months will be considered as intensive phase.)

^b The terms “conversion” and “reversion” of culture as used here are defined as follows :

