Conversion (to negative): culture is considered to have converted to negative when two consecutive cultures, taken at least 30 days* apart, are found to be negative. In such a case, the specimen collection date of the first negative culture is used as the date of conversion. (*According to intervals of research visits, it will be 4 weeks)

Reversion (to positive): culture is considered to have reverted to positive when, after an initial conversion, two consecutive cultures, taken at least 30 days* apart, are found to be positive. For the purpose of defining Treatment failure, reversion is considered only when it occurs in the continuation phase. (*According to intervals of research visits, it will be 4 weeks)

7. Study Timeline

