7.1. Control arm

	Screening	Baseline Visit ¹	Treatment						End of Treatment ⁷	End of Study
Weeks (w)	-2w ~ 0d	0	1w	2w	4w	8w	12w~ (Every 4w)	52w~ (Every 2month)	80w~	24month
Visit window	n-a	n-a	±4d	±4d	±1w	±2w	±2w	±2w	±2w	±2w
Consent	O									
Randomization		O								
Medical history	O									
Physical Exam	O		O	O	O	O	O	O	O	O
Neurologic exam	O									
Sputum AFB smear	O ⁵	O ⁵	O	O	O	O	O	O	O	O
TB culture (solid)	O ⁵	O ⁵	O	O	O	O	O	O	O	O
TB culture (liquid)	O ⁵	O ⁵	O	O	O	O	O	O	O	O
Genotypic DST	If available									
Phenotypic DST ²	With first/reverted cultured M.TB									
Chest X-ray (CXR)	O ⁵	O ⁵	O ⁸	O ⁸	O	O	O	O	O	O
Chemistry, Electrolyte	O ⁵	O ⁵	O	O	O	O	O	O	O	
Complete blood count	O ⁵	O ⁵	O	O	O	O	O	O	O	
ECG	O ⁵									
Urine HCG ³	O	O								
HIV, HBV ⁴		O ⁵								
Optic test	O									
Compliance of drug intake			O	O	O	O	O	O	O	
Adverse drug reaction			O	O	O	O	O	O	O	
Other medication ⁶	O	O	O	O	O	O	O	O	O	

¹Administration of anti-TB regimen can begin at baseline visit since drug-resistant TB must be treated immediately.

²Drug susceptibility test for isoniazid, rifampicin, ethambutol, pyrazinamide, streptomycin, kanamycin, amikacin, capreomycin, ofloxacin, levofloxacin, moxifloxacin, prothionamide, cycloserine, and para-aminosalicylic acid (omit for patients with results already provided).

³Only for childbearing age (the blood HCG test result can be extracted)

⁴Study drugs can be administered before the obtaining of results since eligibility is not determined by these results.

⁵Could be skipped if previous tests except ECG were done within four weeks. In case of ECG, within 1week.

⁶Check prohibited drugs for exclusion criteria at screening visit, and check immunosuppressants including steroids after enrollment.

⁷End of treatment(EOT) visit will be determined by the standard TB treatment guidelines. If EOT visit and the end of study(EOS) visit are the same, a test corresponding to the EOT visit will be conducted.

⁸Could be skipped if previous CXR test was performed within 2 weeks

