3.2 Handling of Missing Data

When categorized as 'loss to follow-up', 'withdrawal', or 'withdrawal of consent' will be considered as below.

- ① 'Treatment failure' in the case of dropping out due to 'loss to follow-up', 'investigator's decision', 'withdrawal of consent', 'treatment failure', or 'death' during the treatment
- ② 'Not accessible' in the case of dropping out due to 'pregnancy' during the treatment
- ③ 'Treatment failure' in the case of dropping out due to 'relapse' after the treatment completion. However, reinfection by other strain is 'not assessable'.
- ④ 'Not accessible' when there is no evidence of treatment failure, such as bacteria reversion in the case of withdrawal due to 'loss to follow-up', 'investigator's decision', 'withdrawal of consent', 'pregnancy', or 'death' after the treatment completion

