4.1 Subject Participation Status in Clinical Trial

The subject distribution can be summarized as follows as the result of the clinical trial (Figure 1 and Table 1).

[figure not shown]

Figure 1. Subject Enrollment Distribution

Table 1. Clinical Trial Results

	Investigational Arm	Control Arm
Enrollment, n	xx	xx
Non administration of study drug	xx	xx
No randomization due to screening failure	xx	xx
Violation of inclusion/exclusion criteria	xx	xx
Violation of the inclusion criterion 1	xx	xx
Violation of the inclusion criterion 2	xx	xx
Violation of the inclusion criterion 3	xx	xx
Violation of the exclusion criterion 1	xx	xx
Violation of the exclusion criterion 2	xx	xx
Violation of the exclusion criterion 3	xx	xx
Violation of the exclusion criterion 4	xx	xx
Violation of the exclusion criterion 5	xx	xx
Violation of the exclusion criterion 6	xx	xx
Violation of the exclusion criterion 7	xx	xx
Violation of the exclusion criterion 8	xx	xx
Fluoroquinolone resistance confirmed during the study	xx	xx
Rifampicin mono-resistance confirmed during the study	xx	xx
Rifampicin susceptibility confirmed during the study	xx	xx
mITT analysis group, n	xx	xx
Treatment of less than 80% throughout the planned period	xx	xx
Withdrawal or death before treatment completion (less than 80% of the planned period)	xx	xx
Investigator's judgment that participating in the study is not beneficial to the subject	xx	xx

Withdrawal of consent	xx	xx
Treatment failure	xx	xx
Pregnancy	xx	xx
Death	xx	xx
Non-execution of sputum testing before culture conversion to negative	xx	xx
Administration of study drug in the control arm	xx	xx
PP analysis group, n	xx	xx

※ Safety analysis (per the administration of study drugs)

	Investigational Arm	Control Arm	Total
Number of enrollments, n	xx	xx	xx
Non-administration of study drug	xx	xx	xx
Safety analysis (per the administration of study drugs), n	xx	xx	xx
Administration of Delamanid or linezolid	xx	xx	xx
No administration of Delamanid or linezolid	xx	xx	xx

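### The SAP's mITT exclusion for fluoroquinolone resistance is not limited to the strain present at enrolment, so a failure with resistance acquired later could drop out of the primary analysis set

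*Combined protocol and SAP*

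**What the plan says.** **SAP.** Section 3.1 defines mITT as randomised, eligible, treated at least once, and then adds: "The subjects are not confirmed to be additionally resistant to fluoroquinolone, mono-resistant to rifampicin, or susceptible to rifampicin". Section 5 repeats the sentence. Table 1 in SAP 4.1 carries the row "Fluoroquinolone resistance confirmed during the study", together with rows for rifampicin mono-resistance and rifampicin susceptibility, all above the mITT line. SAP 3.2 item 1 assigns failure to drop-outs during treatment (loss to follow-up, investigator's decision, withdrawn consent, treatment failure, death). Item 3 assigns failure for "relapse' after the treatment completion. However, reinfection by other strain is 'not assessable".

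**Protocol outcome definitions.** In 6.4, failure requires "Treatment terminated or need for permanent regimen change of at least two anti-TB drugs because of" one of four grounds. One ground is "Evidence of additional acquired resistance to fluoroquinolones or second-line injectable drugs". Another is bacteriological reversion, with the restriction "For the purpose of defining Treatment failure, reversion is considered only when it occurs in the continuation phase". Section 6.3 defines reversion more loosely, as MTB that "is cultured at least two or more times after negative conversion", with no time limit.

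**Protocol testing and withdrawal.** In both arms the schedule places phenotypic susceptibility testing "With first/reverted cultured M.TB". Section 8.1 says the same, if a specimen is available. Section 8.7 item 5 withdraws participants on additional results showing fluoroquinolone resistance, rifampicin mono-resistance or rifampicin susceptibility.

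**Protocol analysis set.** The mITT definition in 10.2 contains no explicit resistance exclusion.

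**The concern.** Resistance present at enrolment means the participant was outside the target population, and excluding such people in both arms is defensible. Resistance that emerges after randomisation is different: it can be a consequence of the regimen, and the protocol treats it as a possible ground for failure. The SAP wording does not separate the two. A participant could therefore meet the trial's own definition of failure and, because of the same laboratory result, leave the denominator of the primary comparison. No text says which rule comes first. The trial is open-label, so membership of the primary set should not depend on how a sentence is read once outcomes are known.

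**Working it through.** **1. Which participants the wording reaches**

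| Situation | Outcome rule | SAP mITT wording |
|---|---|---|
| Enrolment isolate resistant, result reported late | Not an outcome event | Excluded (likely intent) |
| Enrolment isolate susceptible, reverted isolate on treatment resistant | Failure if protocol 6.4 is met, or under the drop-out rule in SAP 3.2 item 1 and protocol 10.2 2) item 1 | Also excluded as written |
| Relapse after completion, relapse isolate resistant | Failure under SAP 3.2 item 3 | Could be excluded, if a relapse culture is treated as a reversion under 6.3 and is tested |

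The second row can arise under the planned schedule, because reverted cultures are tested in both arms. The third row is less certain. It needs relapse to be read as reversion, a specimen to be available, a resistant result, and an analyst who lets the general exclusion override the specific relapse rule. In either row, the failure rules do not bring back someone who is already outside mITT.

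**2. The plan's own sample size**

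Inputs (protocol 10.1, SAP 2.3.1): control 80%, investigational 90%, margin -10 points, one-sided 0.025, power 80%.

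n = (1.960 + 0.842)² × (0.9×0.1 + 0.8×0.2) / (0.10 + 0.10)² = 7.849 × 0.25 / 0.04 = 49.06, so 50 by this formula against the stated 48. That is close enough. Inflation: 48 / (0.50 × 0.95) = 101.05, giving the stated 102 per arm.

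**3. Effect of removing one failure**

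The documents give no rate of acquired resistance, so these counts are assumed, with 48 per arm. The SAP names no interval method; I use the Wald lower limit: d − 1.96 × √[p₁(1−p₁)/n₁ + p₀(1−p₀)/n₀].

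First row: d = 0.8333 − 0.7917 = 0.0417, SE = 0.0796, limit = 0.0417 − 0.1560 = −0.1143.

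| Investigational | Control | Removed | Lower limit | Non-inferior |
|---|---|---|---|---|
| 40/48 | 38/48 | none | -11.4% | no |
| 40/47 | 38/48 | one investigational | -9.4% | yes |
| 40/48 | 38/47 | one control | -12.9% | no |
| 40/47 | 38/47 | one from each | -10.9% | no |
| 43/48 | 38/48 | none | -4.0% | yes |
| 43/47 | 38/48 | one investigational | -1.7% | yes |
| 43/48 | 38/47 | one control | -5.5% | yes |

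With Newcombe intervals the first two limits are -11.6% and -9.8%, so the conclusion changes there too.

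The neighbouring counts show how narrow this is. With control at 38/48, 39/48 moves only from -13.9% to -11.9% when one investigational failure is removed, and 41/48 is already non-inferior at -9.0%. Only 40/48 changes to non-inferior. Removing one control failure works the other way: 41/48 against 38/47 gives -10.5%.

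**4. Over all possible results**

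Exact binomial enumeration, 48 per arm, Wald rule, exactly one failure removed where one exists:

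| True rates (investigational v control) | None removed | One investigational | One control | One from each |
|---|---|---|---|---|
| 90% v 80% | 81.2% | 87.6% | 74.6% | 83.0% |
| 70% v 80% (at the margin) | 2.7% | 4.3% | 1.9% | 3.1% |

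Entries are the probability of concluding non-inferiority. Each removal pattern is an assumption; if nobody is affected, the first column applies.

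**The case against.** The strongest reply is that the context already settles the meaning. Entry is allowed on a genotypic rifampicin result alone, genotypic testing for fluoroquinolone resistance is done only if available, and exclusion criterion 1 covers only known resistance. Late results on enrolment isolates are therefore expected. The 50% inflation for fluoroquinolone-susceptible disease makes sense only if those participants are later removed. In Table 1 the row stands beside two facts about the enrolment strain, and the reference there to the study period can describe when the result was confirmed rather than when resistance arose. Protocol 8.7 item 5 speaks of additional test results, which fits the SAP's adverb.

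Most of this stands as evidence of intent, and it lowers the severity. It does not settle the text, because the same adverb also echoes the acquired-resistance ground in 6.4 and no sentence names the isolate.

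Three stronger readings are tempting, and the documents do not support them:

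- *The SAP means to delete acquired-resistance failures.* Nothing says so, and the surrounding text points the other way.
- *The wording favours the new regimen.* The direction is unknown. Time on treatment is longer in the control arm (20 to 24 months against 9 or 12), while two-monthly cultures after treatment end are scheduled only in the investigational arm (8.4.2).
- *A participant on treatment can fail only through 6.4.* SAP 3.2 item 1 and protocol 10.2 2) item 1 also assign failure to other drop-outs.

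Nor is the protocol in plain conflict with the SAP: 10.2 omits the exclusion, but the sample size in 10.1 presupposes one.

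**Conclusion.** The point holds as a narrow but real gap in a rule that decides the primary denominator. Followed literally, the SAP can remove a participant whom the protocol counts as a failure. The on-treatment case with a reverted, resistant isolate is the clear one; the relapse case is possible but less certain. The number affected may be zero and the direction cannot be stated.

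The calculations rest on assumed counts, 48 per arm and a Wald interval. They show that a single participant can decide the result at the margin and that the rule is immaterial away from it. The shifts in section 4 of the working are conditional on exactly the removals stated there and are not forecasts. Severity is minor to should-fix, mainly because the correction is cheap.

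**What to change.** In SAP 3.1, SAP section 5 and the three Table 1 rows, limit the exclusion, identically in both arms, to fluoroquinolone resistance, rifampicin mono-resistance or rifampicin susceptibility shown *in an isolate collected on or before the start of study treatment, whenever the result is reported*. Add that participants whose resistance is first shown in an isolate collected after that date stay in mITT, with their outcome assigned by protocol 6.4 and SAP 3.2, including the reinfection rule.

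Add one sensitivity analysis that excludes participants who have no tested isolate from on or before treatment start and whose first tested isolate is resistant.

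At the next amendment, reconcile protocol 8.7 item 5, protocol 10.2 and SAP 3.2 with this definition. This concerns how such participants are counted; it does not ask for any particular withdrawal rule.

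**Cost.** One clause and one sentence in the SAP definition (stated in two places), three row labels and one extra analysis. The protocol changes need the procedure in 14.1. Isolate collection dates may have to be retrieved from laboratory reports, since the documents do not say whether the CRF holds them. A few participants with unverified enrolment susceptibility will stay in mITT, and the success rate may be slightly less favourable.
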